7. EFFICACY

All efficacy endpoints will be listed but not summarized.

7.1. Primary Efficacy Endpoint

The primary efficacy endpoint and efficacy endpoints will be derived and listed but not summarized.

Objective Response Rate

A subject's BOR is determined by the highest qualitative value assessed during the study given a hierarchy of overall response results: CR > PR > SD > PD > NE. Response will be defined according to RECIST v1.1. In order for a valid value of SD to be assigned, there must be evidence of stable disease for at least 6 weeks. If the minimum time for SD has not been met on the first assessment, the assignment of BOR will depend on subsequent response assessments.

Sponsor: Aduro Biotech, Inc.
Protocol Number: ADU-CL-14
Version and Date: Version 1.0, 13Mar2018

Subjects which do not have follow up data after a first assessment of SD prior to the minimum time requirement will be considered as not evaluable. BOR will be based on assessments collected after the first dose of study until disease progression; assessments collected after the start of new cancer treatment will not be considered.

Objective response is achieved for subjects who have a BOR of CR or PR according to RECIST v1.1. ORR is defined as the number of subjects who exhibit a BOR response of CR or PR divided by the number of subjects evaluable for analysis and will not be summarized or reported in the CSR synopsis.

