Evaluable Analysis Set (EAS) is defined as all subjects who received at least 1 dose of CRS-207 and have at least one evaluable post-baseline RECIST tumor response assessment or were discontinued due to toxicity. The EAS will be the primary analysis set for the analyses of tumor-related endpoints (ORR, DCR, DOR, and PFS).

AE data will be coded to system organ class and preferred term using Medical Dictionary for Regulatory Activities (MedDRA; Version 18.1, or later). The number and percentage of subjects experiencing any TEAE, overall, and by system organ class and preferred term will be tabulated. The incidence rates adjusted by cumulative exposure will also be presented overall and by cycle. AEs associated with clinical laboratory parameters will be characterized according to NCI CTCAE, Version 4.03. Shifts in toxicity grades from baseline to each visit will be summarized.

Disease responses as determined by RECIST will be summarized by response level at each visit and best overall response. The ORR and DCR, along with a 95% CI will be summarized. PFS, DOR, and OS will be summarized using Kaplan-Meier methods.

SAMPLE SIZE DETERMINATION

This study is descriptive in nature, as such the sample size for this study is determined by practical rather than statistical considerations. Approximately 79 subjects will be enrolled with evaluable post-baseline tumor data. With 79 subjects, the precision for point estimate for ORR is as follows: the 95% CI width for ORR based on Wilson score intervals are at most the observed proportion +/- 0.108. If the observed ORR = 30.4% (24 of 79 subjects with PR or CR), the lower bound of the 95% CI would be 19.5%.

Table 1-1 Schedule of Events: Same-day (D1) Dosing Regimen

Study Phase	Screen	Cycle 1 [1]				Cycle 2 [1]				Cycle 3 [1]			Cycle 4 [1]		Cycle 5 and all future odd numbered cycles [1]		Cycle 6 and all future even numbered cycles [1]		EOT [2]	Follow-up	
Study Day	-28 to -1	1	2	3	7	1	2	7	15	1	2	7	1	7	1	1	1	1	±7		
Visit Window (days)	-	-	-	-	±1	±3	±1	±1	-7	±3	±1	±1	±3	±1	±3	±3	±3	±3			
Study Procedures																					
Informed Consent	X																				
Inclusion/Exclusion Criteria	X	X																			
Medical History, Height	X																				
Archived Tumor Specimen [3]	X																				
Tumor Biopsy [4]	X									X											
CT Tumor Evaluation [5]	X										X						X		X		
Survival, additional treatment [6]																				X	
ECOG Performance Status	X	X				X				X			X		X		X		X	X	

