6.5.4 Analysis Sets

Evaluable Analysis Set (EAS) is defined as all subjects who received at least 1 dose of CRS-207 and have at least one evaluable post-baseline RECIST tumor response assessment or were discontinued due to toxicity. The EAS will be the primary population for analyses of tumor-related endpoints (ORR, DCR, DOR, and PFS).

Full Analysis Set (FAS) is defined as all subjects who received at least 1 dose of CRS-207. The FAS will be used for analyses of OS, immunogenicity and other biomarker data, and sensitivity analysis of select tumor-related endpoints.

Safety Set (SAF) includes all subjects who received any study treatment (pembrolizumab or CRS-207). The SAF will be used for all analyses of safety data and may be used for select biomarker data.

Additional analysis sets (e.g. per protocol set) may be defined in the SAP.

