6.5.5.1 Primary Efficacy Variable and Analysis

The ORR is defined as the proportion of subjects with best overall response (BOR) of partial response (PR) or complete response (CR) according to RECIST v1.1. The proportion of subjects with ORR in the EAS, along with a 95% CI based on the Wilson Score interval, will be reported. Analyses of ORR described above may be repeated in FAS, treating missing BOR as a non-responder. Objective disease response at each visit and best overall response will also be summarized using the EAS.

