3.5. Timing of Analyses

On 12 December 2017, Aduro decided to cease development activities of CRS-207 and close out ongoing studies. As of 31 January 2018 every subject had completed their end of treatment visit. No additional follow-up of these subjects is expected. This ASAP details the analysis plans for the CSR synopsis as of the final database lock.

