6. STUDY SUBJECT DATA

6.1. Analysis Sets

The Safety Analysis Set (SAF) includes all subjects who received any study treatment. All analyses of safety data will be conducted using the safety set. The SAF is the only analysis set used for all listings and analysis.

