11. CHANGES TO THE PLANNED ANALYSIS

All efficacy endpoints will be derived and listed for each subject, but will not be summarized.

Sponsor: Aduro Biotech, Inc.
Protocol Number: ADU-CL-14
Version and Date: Version 1.0, 13Mar2018

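### The SAP, dated after every subject had finished treatment, drops without a stated reason the summaries of ORR and all other efficacy endpoints that the protocol promised

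*SAP*

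**What the plan says.** Protocol 6.5.5.1 commits to the primary analysis: "The proportion of subjects with ORR in the EAS, along with a 95% CI based on the Wilson Score interval, will be reported". It allows a repeat in the FAS with a missing best overall response (BOR) counted as non-response. The synopsis repeats the commitment ("The ORR and DCR, along with a 95% CI will be summarized") and extends it to the time-to-event endpoints: "PFS, DOR, and OS will be summarized using Kaplan-Meier methods". Protocol 6.5.4 defines the EAS and FAS and makes the EAS primary for tumor-related endpoints.

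SAP version 1.0, dated 13 March 2018, withdraws these summaries. Section 7.1 states: "The primary efficacy endpoint and efficacy endpoints will be derived and listed but not summarized". Sections 7.1 and 7.2 add that ORR and DCR will be neither summarized nor reported in the CSR synopsis, and section 2 plans no summary tables for OS, PFS, duration of response or tumor response. Section 6.1 leaves one population: "The SAF is the only analysis set used for all listings and analysis". Section 11 declares the change: "All efficacy endpoints will be derived and listed for each subject, but will not be summarized". It gives no reason.

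On timing, SAP 3.5 records the sponsor's decision of 12 December 2017 to stop CRS-207 development, and then: "As of 31 January 2018 every subject had completed their end of treatment visit".

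**The concern.** The primary efficacy variable was prespecified together with its estimator, interval and population. The plan that governs the final report removes that estimate at a time when responses could already be known: treatment was open-label and local investigators assigned response. A reader of the CSR synopsis would learn how many subjects had adverse events, laboratory shifts or died, but not how many responded.

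Two things are at stake. The trial would leave its own primary efficacy question unanswered in the synopsis. And dropping a prespecified endpoint after the data exist, without giving a reason, exposes the sponsor to a suspicion of outcome-driven reporting that a one-line result would remove. In addition, SAP 7.1 divides responders by the subjects evaluable for analysis, but no analysis set in the SAP says who they are. Anyone counting from the listings would have to choose a denominator.

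**Working it through.** **1. The protocol's own precision figure.** Protocol 6.5.1 gives a Wilson 95% interval of at most ±0.108 with 79 subjects. The Wilson half-width is z·√(p(1−p)/n + z²/4n²) / (1 + z²/n), which at p = 0.5 becomes z / (2√(n + z²)). With z = 1.96 and n = 79: 1.96 / (2√82.84) = 0.1077. This reproduces. The ±0.134 for n = 50 also reproduces (0.1336). For n = 29 I obtain 0.171 against the stated 0.173. For 24/79 the Wilson interval is 21.3% to 41.2%, whereas the stated lower bound is 19.5%; subtracting 10.8 points from 30.4% gives 19.6%. These small discrepancies do not bear on this point.

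**2. Promise against plan.**

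| Item | Protocol | SAP |
|---|---|---|
| ORR | n/N with Wilson 95% CI in EAS (6.5.5.1) | derived, not summarized, not in CSR synopsis (7.1) |
| DCR | same manner as ORR (6.5.5.2) | same exclusion (7.2) |
| PFS, DOR, OS | Kaplan-Meier (synopsis, 6.5.5.2) | listed only (2, 7.2) |
| Analysis sets | EAS, FAS, SAF (6.5.4) | SAF only (6.1) |

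**3. Table count, SAP 13.1.** Four tables numbered 14.1.x, five 14.3.1.1.x, two 14.3.1.2.x, two 14.3.2.x and two 14.3.4.x: 4 + 5 + 2 + 2 + 2 = 15. None is an efficacy table. SAP 13.3 plans no figures.

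**4. Timing.** From 31 January to 13 March 2018 is 28 + 13 = 41 days, so the SAP is dated at least 41 days after the last end-of-treatment visit. Protocol 6.5.8 sets the final analysis for when all subjects have completed six cycles, or have stopped treatment and completed that visit. By SAP 3.5 this condition was met.

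**5. What the omitted result could look like.** Neither document gives enrolment at closure, so n is an assumption here. The zero-responder upper limit is z²/(n + z²); for n = 10, 3.84/13.84 = 27.8%. For one responder in 10, the centre is (0.1 + 0.192)/1.384 = 0.211 and the half-width 1.96·√(0.0090 + 0.0096)/1.384 = 0.193, giving an upper limit of 40.4%.

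| Assumed n | Largest half-width | Upper limit, 0 responders | Upper limit, 1 responder |
|---|---|---|---|
| 5 | 0.326 | 43.4% | not computed |
| 10 | 0.263 | 27.8% | 40.4% |
| 15 | 0.225 | 20.4% | 29.8% |
| 20 | 0.201 | 16.1% | 23.6% |

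**6. Obstacles to a PFS summary.** SAP 5.7 assumes imaging every 8 weeks and sets a lapse window of 2 × 8 × 7 = 112 days. SAP 3.1 and the protocol image about every 6 weeks, for which the same rule gives 2 × 6 × 7 = 84 days. SAP 7.2 first censors deaths after the window at the latest adequate assessment, and then at first dose. These statements have to be reconciled before PFS is summarized. SAP 11 also says all efficacy endpoints will be derived, while SAP 7.3 says the irRECIST versions will not.

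**The case against.** The best defence is that this is an orderly close-out. The sponsor ended the whole CRS-207 programme and the SAP is an abbreviated plan for a synopsis. The study is descriptive, with no hypothesis test and a sample size set on practical grounds, and protocol 6.5 describes its analyses as a guide. All efficacy summaries are dropped, whichever way they might point, and section 11 says so. Listings of tumor response, lesions, PFS, duration of response, OS and survival follow-up remain. Duration of response is computed only for responders, so its listing would identify them. Deaths are still tabulated, including those in post-study surveillance (SAP 10.1).

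Much of this stands. A reader might infer selective outcome reporting. The documents do not support that: nothing shows when the choice was made or that responses influenced it, and the omission is uniform and disclosed. Nor is all trace of efficacy removed; what goes is the summary, its interval and its denominator.

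The defence does not justify the omission itself. A descriptive study has no power to lose, so fewer subjects only widen the interval. The protocol's trigger for the final analysis was met. The SAP does not treat small numbers as a bar elsewhere: section 4 produces by-visit summaries from two subjects upward.

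**Conclusion.** The point holds as an unexplained omission, decided after the data existed, of the prespecified primary efficacy result and all secondary efficacy summaries, together with the loss of the sets that define the denominator. It should be fixed. It is not evidence of misconduct, and no confirmatory claim is lost.

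Its size is 0 efficacy displays among 15 tables and no figures. How informative the missing estimate would be cannot be determined, because enrolment and responses are not stated. It is tempting to argue that even a small trial without responses would rule out a benchmark. The documents do not support this. It requires zero responders, and a single response in 20 raises the upper limit to 23.6%, above the 22% benchmark in protocol 6.1.1. That benchmark comes from PD-L1-expressing third-line patients, and the second-line range there is 7% to 28%. The 30.4% in protocol 6.5.1 only illustrates an interval and is not a target. The limits tabulated above are therefore illustrations and exclude nothing.

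The conclusion rests on the SAP's scope as written, that is, the CSR synopsis as the report of the final analysis.

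**What to change.** - In SAP 6.1, restore the EAS and FAS as protocol 6.5.4 defines them.
- Add one table to the CSR synopsis: BOR counts, and ORR and DCR as n/N with Wilson 95% intervals. Keep the EAS primary, as the protocol does, with the FAS beside it counting missing BOR as non-response. Making the FAS primary now would be a new post-data choice.
- Report numbers of events and censored subjects for PFS, duration of response and OS, with Kaplan-Meier medians where estimable. First reconcile the lapse window and the two rules for deaths after it (SAP 5.7 and 7.2) with the protocol's six-weekly imaging.
- Label the results as estimation only after early termination.
- In SAP 11, give the reason for anything still omitted, and reconcile that section with 7.3 on the irRECIST endpoints.

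The cost is one or two tables from variables that the SAP already derives, plus the work of settling the censoring rule. The downside is wide intervals that need a caveat. Because no further follow-up is expected, against at least 12 months planned, some medians may not be estimable.

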6.4.2.1 Tumor Imaging and Response Assessments

Computed tomography (CT) scans of the chest, abdomen and pelvis will be performed at screening (pre-treatment baseline assessment) within 28 days of first dose of study drug and at approximately 6 week intervals after initiation of study drug using the same assessment technique. If CT scan is contraindicated (e.g. allergy to contrast dye), magnetic resonance imaging (MRI) should be performed. Subjects with previously treated brain metastases must be stable (without evidence of progression by imaging at least 4 weeks prior to the first dose of study drug and neurologic symptoms have returned to baseline), have no evidence of new or enlarging brain metastases. Radiographic tumor evaluation should include CT of all affected sites.

For each scan, tumor measurements should be obtained using RECIST v1.1 and assessment of response determined by the local Investigator. The investigator/local radiology review will also use irRECIST ([Section 11](#)) to assess tumor response and progression, and make treatment decisions. If radiographic disease progression is observed, another scan should be done at least four weeks later to confirm disease progression prior to treatment discontinuation. Subjects discontinued after confirmation of progression will enter the Follow-Up Period. Subjects that discontinue all study drugs and complete the EOT without documented progressive disease (based on RECIST v1.1) will be asked to complete tumor imaging every 6 weeks until documented disease progression or start of another anticancer therapy.

The method of assessment and technique should be consistent throughout the study to enable characterization of each identified and reported lesion.

For subjects on treatment more than 12 months, the frequency of imaging may be reduced to every 12 weeks.

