Tumor imaging and evaluation will be assessed at Screening and during the Treatment and Evaluation Period approximately every 6 weeks after initiation of study drug. Tumor measurement and assignment of response will be determined by local Investigators. For subjects on treatment more than 12 months, the frequency of imaging may be reduced to every 12 weeks. Peripheral blood will be collected to assess immune responses directed against *Listeria monocytogenes*, mesothelin, and other tumor-associated antigens. Archived tumor tissue and paired tumor biopsies (collected at Screening and during Cycle 2) will be used to explore the association of PD-L1 expression, mesothelin expression, and TIL characteristics with clinical responses.

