OS is defined as the number of weeks from the date of first dose of study treatment to the date of death from any cause and is computed as described in Section 5.3. Subjects still alive as of the data cut-off date will be censored on the last known alive date from mortality status follow up. For subjects that are lost to follow up, the last visit in the database or last contact date where the subject is documented to be alive will be used to estimate last known date alive.

OS will be listed.

Duration of Response

DOR will be computed for subjects who have been identified as a responder (achieved an overall response of CR or PR according to RECIST v1.1 during the PFS observation period); it will be computed as described in Section 5.3, where the reference date will be the first date where a subject has been documented to have achieved a responder designation. Censoring algorithms similar to those identified for PFS will be used for DOR.

DOR will be listed.

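### A single investigator-read CR or PR counts as an objective response and enters DOR with no confirming scan, which on balance inflates response

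*SAP*

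**What the plan says.** - **Response.** SAP 7.1 ranks CR > PR > SD > PD > NE and states: "A subject's BOR is determined by the highest qualitative value assessed during the study". Assessments count from first dose until disease progression, and those after new cancer treatment are excluded. An objective response is a BOR of CR or PR. Protocol 6.5.5.1 defines ORR on the same BOR.
- **Criterion.** SAP 7.1 adds: "Response will be defined according to RECIST v1.1". It does not mention confirmation.
- **Stable disease.** The same section does set a minimum for SD: "there must be evidence of stable disease for at least 6 weeks". CR and PR have no counterpart.
- **DOR.** SAP 7.2 computes DOR for a subject who has "achieved an overall response of CR or PR according to RECIST v1.1 during the PFS observation period", starting when responder status is first documented.
- **Readers.** SAP 3.1: "Tumor measurement and assignment of response will be determined by local Investigators". Protocol 6.3.3 says that nobody at the sites is blinded. No central review is described.
- **Progression.** Protocol 6.4.2.1 says that after radiographic progression "another scan should be done at least four weeks later to confirm disease progression prior to treatment discontinuation". For PFS, protocol 6.5.5.2 uses the first documented RECIST progression, and SAP 7.2 uses the earliest progressive-disease finding.
- **Reporting.** SAP 7, 7.1 and 11 derive and list efficacy endpoints. ORR is neither summarized nor reported in the study report synopsis.

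**The concern.** Read literally, a subject with PR at one scan and SD at the next is a responder, and DOR runs from that one PR. The best of several readings is a maximum. A subject near the 30% shrinkage threshold needs only one favourable error to cross it, and later scans that disagree do not undo the result. The reader knows the treatment.

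There is no control arm to absorb this. Protocol 6.1.1 wants to judge the responding proportion against outside checkpoint-inhibitor data and gives 22% as its third-line benchmark. Protocol 4.2 shows that 22% came from central review, while investigator review of the same study gave 33%. That 11-point gap does not isolate confirmation, but it shows how far the method of reading can move a response rate. False responders also add durations to DOR that do not describe a response.

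**Working it through.** **Yardstick.** The plan's maximum 95% Wilson half-width for 79 subjects is z/(2√(n+z²)) = 1.96/(2√(79+3.84)) = 0.1077. This reproduces the stated 0.108. The interval covers sampling error only, not reading error.

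**Inputs from the documents.** Scans are about every 6 weeks. The final analysis in protocol 6.5.8 follows six 3-week cycles or discontinuation, so 18/6 = 3 scans for a subject who completes six cycles. The planned size is 79 and the benchmark ORR is 22%.

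**Assumed inputs.** The documents give no reading error, false-response rate or tumour trajectory. All of these are assumptions.

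**Check A: closed form.** Let p = 0.22 be the true ORR and q the chance of a false PR per scan in a non-responder. Scans are independent and no true responder is missed.
- Single scan: p + (1−p)[1−(1−q)³]
- Two consecutive scans: p + (1−p)(2q²−q³)

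| q | Single scan | Two scans | Single-scan excess in 79 |
|---|---|---|---|
| 1% | 24.3% | 22.0% | 2.3% × 79 ≈ 2 |
| 2% | 26.6% | 22.1% | 4.6% × 79 ≈ 4 |
| 5% | 33.1% | 22.4% | 11.1% × 79 ≈ 9 |

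**Check B: simulation, changing tumours.** True ORR is 22%. Error is symmetric at baseline and at each of three scans. PR is a fall of 30%, PD a rise of 20% from nadir, and BOR stops at first PD.

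| Error SD | Single-scan ORR | False responders gained | True responders lost | Net | Confirmed ORR |
|---|---|---|---|---|---|
| 5% | 22.3% | 0.5 | 0.2 | +0.3 | 21.0% |
| 10% | 24.4% | 3.1 | 0.7 | +2.4 | 19.0% |
| 15% | 28.6% | 8.0 | 1.4 | +6.6 | 18.3% |

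**Check C: simulation, stable true change.** The SD of true change is 42%, with three scans. This leaves more subjects near the threshold.

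| Error SD | True ORR | Single scan | Net | Confirmed | Net |
|---|---|---|---|---|---|
| 5% | 23.7% | 26.3% | +2.6 | 22.3% | −1.4 |
| 10% | 23.7% | 29.6% | +5.9 | 20.4% | −3.3 |
| 15% | 23.9% | 33.7% | +9.8 | 18.8% | −5.1 |

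A fourth scan at 15% error gives 35.1%, or +11.2.

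**Reading the results.** For 5–15% error and three scans, the net excess is +0.3 to +9.8 points. On 79 subjects that is 0.2 to 7.7 responders. The direction is the same throughout and the size depends on the assumed tumour course. The confirmed rule errs low. In Check B it misses by 1.0 and 3.0 points at 5% and 10% error, which is more than the single-scan rule (0.3 and 2.4). At 15% error, and throughout Check C, it is closer to the truth.

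**The case against.** **Confirmation of progression.** A reader might infer that progression must be confirmed while response need not be, so that the endpoint is lopsided by design. The documents do not support this. The repeat scan in protocol 6.4.2.1 and Section 11 governs whether treatment continues under irRECIST. Protocol 6.5.5 bases the primary analyses on RECIST, endpoint progression counts from the earliest scan that shows it, and SAP 7.3 does not derive irRECIST endpoints. Some looseness remains. SAP 7.1 does not say which progression closes the BOR window, and Section 11 of the protocol links irRECIST decisions to the ORR endpoint.

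**Direction of error.** A reader might also infer that error can only add responders. It cannot only add. A false PD closes the BOR window before a later response, and a true PR can be measured short of threshold. Check B shows 0.2 to 1.4 points lost this way.

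**No reported ORR.** Under the SAP no ORR estimate is produced, and the visit-level response and lesion listings let a reader see whether a PR persisted. This stands and limits the consequence. BOR and DOR are still derived under the single-scan rule.

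**Close-out.** SAP 3.5 records that development ceased, that every subject had completed the end-of-treatment visit by 31 January 2018, and that no more follow-up is expected. Late responses may therefore never be confirmable. This stands and argues against replacing the rule outright.

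**RECIST v1.1 by reference.** Whether the citation itself imports a confirmation rule, and whether the benchmark rates were confirmed, cannot be settled from the documents. That is a reason to state the rule. A second scan read by the same investigator also does not remove unblinded-reader bias.

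**Conclusion.** The point holds in a limited form. As written, one unblinded investigator reading of CR or PR before progression makes a responder for BOR, ORR and DOR, although SD must last 6 weeks. The effect is upward on balance, not solely upward. The illustrative size is about 0 to 10 points for 5–15% reading error with three scans. It rests entirely on assumed error sizes and tumour courses. The counts on 79 use planned enrolment, and the documents do not give the number treated before close-out. At the upper end the bias is about as large as the planned interval's half-width of 0.108.

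The effect falls on the derived BOR and DOR listings and on any ORR computed under the protocol or from those listings. A reader should not infer that an inflated ORR will appear in the study report synopsis, since none is planned there. Nor should a reader take the confirmed rate as the true one, since it can be further from the truth than the unconfirmed rate.

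**What to change.** In protocol 6.5.5.1 and SAP 7.1 and 7.2:

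1. Derive a confirmed response: CR or PR met again at a scan at least 4 weeks later. Use the existing scans, which are about 6 weeks apart.
2. Show confirmed response beside the unconfirmed BOR, without replacing it.
3. In the tumor response and DOR listings (16.2.6.2.1 and 16.2.6.2.7), flag each response as confirmed, unconfirmed or unconfirmable, the last meaning first seen at the last available scan.
4. Keep the response start date at the first qualifying scan.
5. State that BOR ends at first RECIST progression.

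The cost is wording and derivation work, with no added scans. Confirmed ORR will be lower and can err low, especially with early close-out, which is why both versions should be shown.

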6.2.3 Dosing Eligibility and Delayed Dosing

Subjects must have adequate organ function confirmed (as defined by the laboratory values in Table 6-1) prior to each dosing cycle where CRS-207 is administered; laboratory tests may be performed up to 3 days before dosing.

Table 6-1 Dosing-Eligibility Requirements

Hematologic	Renal	Hepatic
WBC \geq 3000/ μ L	Creatinine \leq 1.5 \times ULN	AST/ALT \leq 5 \times ULN
ANC \geq 1000/ μ L		Bilirubin \leq 1.5 \times ULN OR \leq 3 \times ULN if due to Gilbert's disease
Platelets \geq 90,000/ μ L		
Hemoglobin \geq 8 g/dL		

ALT = alanine aminotransferase; ANC = absolute neutrophil count; AST = aspartate aminotransferase; ULN = institutional upper limit of normal; WBC = white blood cell

Subjects who do not meet dosing eligibility requirements will be monitored; dosing may be delayed up to 2 weeks, after which time it will be considered missed and the subject would continue onto the next scheduled dose. If a dose is delayed more than 2 weeks, contact the Medical Monitor for further instruction on continued dosing.

Pembrolizumab may be administered up to 3 days before or after the scheduled Day 1 of each cycle due to administrative reasons. If subjects on same-day dosing schedule experience severe infusion-related reactions related to the pembrolizumab infusion, the CRS-207 infusion may be delayed to Day 2. CRS-207 must be administered one day after pembrolizumab administration. If the subject experiences a new AE or is recovering from an AE, CRS-207 administration may be delayed up to 7 days and the Sponsor must be notified. If a dose of CRS-207 is delayed beyond 7 days of pembrolizumab, the dose of CRS-207 should be withheld until the next cycle.

Dosing interruptions are permitted in the case of medical / surgical events or logistical reasons not related to study therapy (e.g. elective surgery, unrelated medical events, vacation, and/or holidays). Subjects should be placed back on study therapy within 3 weeks of the scheduled interruption, unless otherwise discussed with the Sponsor. The reason for interruption should be documented in the Subject's study record.

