5.7. Lost to Follow Up or Lapse of Adequate Assessments

If a subject has missed two or more scheduled disease assessments, a censoring date will be required in support of relevant efficacy survival derivations. For example, PFS will be censored at the last adequate disease assessment prior to the lost to follow up window. However, this survival outcome would be considered censored after an extended amount of time without additional assessment (after two have been missed). Based on a protocol specified disease assessment schedule of every other cycle (every 8 weeks, up to 7 days prior to dosing), a lapse window of 112 days would be used to establish a censoring date.

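### The 6-week minimum for stable disease equals the nominal day of the first on-treatment scan, so a permitted but early scan cannot support SD in the listed best overall response

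*SAP*

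**What the plan says.** **The SD rule (SAP 7.1).** Best overall response (BOR) follows a "hierarchy of overall response results: CR > PR > SD > PD > NE". SD carries a minimum: "In order for a valid value of SD to be assigned, there must be evidence of stable disease for at least 6 weeks". For an early first scan the SAP adds: "If the minimum time for SD has not been met on the first assessment, the assignment of BOR will depend on subsequent response assessments". A subject with no further data "after a first assessment of SD prior to the minimum time requirement will be considered as not evaluable".

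**When scans happen.** SAP 3.1 puts imaging "approximately every 6 weeks after initiation of study drug", and protocol 6.4.2.1 gives the same interval. Cycles last 3 weeks. Three places allow movement:
- The protocol's Schedule of Events gives the Cycle 3 Day 1 visit a ±3-day window.
- Protocol 6.2.3 lets dosing move by the same amount: "Pembrolizumab may be administered up to 3 days before or after the scheduled Day 1 of each cycle due to administrative reasons".
- SAP 5.7 describes assessments as falling every other cycle, "up to 7 days prior to dosing". The same sentence calls that interval 8 weeks.

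**How time is counted.** SAP 5.2 takes the first treatment date as the reference for efficacy data. SAP 5.3 counts date minus reference plus 1. SAP 5.6 dates an SD visit by its earliest assessment.

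**What is reported.** The definition of the disease control rate (DCR) in protocol 6.5.5.2 has no minimum SD duration. SAP 7.2 says DCR will not be summarized or reported in the study report synopsis. SAP Section 11 records only that efficacy is derived and listed without summaries. SAP 3.5 describes the close-out: "As of 31 January 2018 every subject had completed their end of treatment visit. No additional follow-up of these subjects is expected".

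**The concern.** A minimum SD duration is normally set a little below the first scheduled scan, so that a scan done within its window can count. Here the two coincide. Two subjects with the same disease course, one scanned on Day 41 and one on Day 43, can receive different BORs because of the appointment date alone.

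At stake is the accuracy of each subject's listed BOR and disease-control status. The listings are the only planned efficacy output, so any later user who tabulates disease control would inherit the distortion. The close-out adds to the concern: with no further follow-up expected, a subject whose last scan was an early SD cannot be reclassified by a later one.

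**Working it through.** The plan states no DCR or SD rate, so there is no figure to reproduce. The check is date arithmetic on the plan's own rules.

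**Start of the clock.** SAP 7.1 does not name it. It does contemplate that the minimum may or may not be met at the first assessment, which makes sense only if time runs from first dose. SAP 5.2 agrees. The minimum is 6 × 7 = 42 days.

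**Nominal scan.** Cycle 3 Day 1 = 1 + 2 × 21 = Study Day 43. Duration is 43 − 1 + 1 = 43 days by the SAP 5.3 count, or 42 elapsed days. Both meet 42, so a scan at the scheduled time passes.

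**Early scans.** Duration in the SAP count equals the study day, so any scan before Day 42 fails.

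| Window applied | Permitted days | Days that fail (SAP count) | Share of days | Share if elapsed days are used |
|---|---|---|---|---|
| ±3-day visit window | 40 to 46 | 40, 41 | 2 of 7 | 3 of 7 |
| Up to 7 days before dosing | 36 to 43 | 36 to 41 | 6 of 8 | 7 of 8 |

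The last column differs because Day 42 is 41 elapsed days. These are counts of calendar days, not probabilities: the documents do not say how scans are spread over the window. If a dose given 3 days early (Day 40) could be combined with a scan 7 days before it, the earliest scan would be Day 33.

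**What happens to an early SD.**
- Next scan SD, PR or CR: disease control is credited as usual.
- Next scan PD: the early SD is not valid, so BOR is PD.
- No later scan: BOR is NE.

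**Direction.** The rule can remove an SD but never add one. Suppose a of n subjects have disease control and one is lost. The rate becomes (a − 1)/n if the subject stays in the denominator, or (a − 1)/(n − 1) if dropped. Both are below a/n whenever a < n. So the direction does not depend on how SAP 7.2 defines evaluable subjects, which it leaves open.

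**The 8-week statement in SAP 5.7.** Every other 3-week cycle is 6 weeks, not 8. On an 8-week interval the scan would be due on Day 1 + 56 = 57 and the earliest permitted day would be 57 − 7 = 50, so a 42-day minimum would never bite. The 112-day lapse window in the same section is 2 × 56; on a 6-week interval it would be 2 × 42 = 84. The SD minimum therefore fits the interval stated in SAP 5.7 but not the one in SAP 3.1 and the protocol.

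**The case against.** The strongest reply is that little depends on this. DCR will not be summarized, no tests are planned, and the listings show the assessments behind each BOR. That stands, and it limits the point to per-subject outcomes.

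A second reply is that the 7-day allowance appears only in the SAP 5.7 sentence that also gives the 8-week interval. The protocol ties scans to first dose and states no 7-day CT window. This also stands: the Day 36-41 range is conditional on that allowance applying to the 6-week schedule. The Day 40-41 range needs only the ±3-day visit window.

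Third, the Schedule of Events appears to include a CT at end of treatment (the table's columns are hard to align in the extracted text). Such a scan could rescue some early SDs before week 12, so it should not be assumed that many subjects had a single scan.

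Fourth, a full 6-week minimum can be defended as conservative: a subject last seen stable on Day 36 has not shown six weeks of stability. That is a legitimate choice, but it should be made knowingly and applied to a schedule that lets subjects meet it. Nothing in the SAP shows that the overlap with the scan date was intended.

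Finally, the SAP is dated 13 March 2018, after all end-of-treatment visits, in an open-label single-arm study. Loosening a threshold then could look data-driven. This is a real cost, and it is met by deriving the number from the scan window and saying so.

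**Conclusion.** The point holds in a limited form. An SD scan that is permitted but falls before Day 42 cannot support SD, and the subject becomes NE or PD unless a later scan shows SD, PR or CR. The affected days are 40-41 under the ±3-day window, or 36-41 if the 7-day allowance applies. This assumes that the SD clock starts at first dose, that SAP 5.3 counting applies, and that the first on-treatment CT belongs to Cycle 3 Day 1. The effect is on derived and listed BOR and disease-control status, and on any later use of them. CR and PR carry no minimum duration, so objective response is untouched.

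Three stronger readings are tempting, and the documents do not support them:
- *SD found on schedule is generally recoded.* A scan on Day 42 or later passes, and an early SD is not recoded automatically.
- *A reported DCR is understated.* No DCR will be reported.
- *The loss is about 3 to 22.5 percentage points.* That range comes from 0.10 × 2/7 = 0.029 and 0.30 × 6/8 = 0.225. The 10% to 30% share of subjects with SD at the first scan and then PD or no scan is assumed, and equal use of every permitted day is assumed too. The documents give neither scan dates nor that share, so the size cannot be determined.

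**What to change.** 1. In SAP 7.1, state that the SD clock starts at first dose, and set the minimum to 6 weeks less the allowed scan window. If the 7-day allowance stands, that is 42 − 7 = 35 days, which admits Day 36. If only the ±3-day window applies, the limit is Study Day 40 (42 − 3 = 39 elapsed days). Giving the limit as a study day avoids the one-day ambiguity between the two counts.
2. State the scan window explicitly, including whether early dosing and an early scan may be combined. If they may, Day 33 is reachable and a 35-day minimum would still miss it.
3. Reconcile the 8-week interval in SAP 5.7, and the 112-day lapse window built on it, with the 6-week schedule in the protocol and SAP 3.1.
4. List the minimum-duration rule in SAP Section 11, since the protocol's DCR definition has none, and record that the number follows from the scan window rather than from the data.

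The cost is a few lines of text and one derivation line. The downside is that SD is credited up to about a week earlier.
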